5.6. Administration and Dosing

5.6.1. Administration of the investigational product

Following randomization, patients will be treated with a daily dose of either 50mg or 100mg ABX464 or will receive placebo.

Treatment groups:

Intervention/treatment Active Arm	
Group #1 (n=20): 100mg qd	2 capsules of 50mg ABX464
Group #2 (n=20): 50mg qd	1 capsule of 50mg ABX464 + 1 capsule of matching placebo
Group #3 (n=20): Placebo	2 capsules of matching Placebo

Patients will be orally dosed in a fed condition (regular breakfast) with a glass of water.

On Day 84 visit, the patient will not take the ABX464-301 study medication (last day of study medication will be on Day 83).

Patient enrolled in the ABX464-302 maintenance study will start the study medication on Day 84 (301 study)/D0 (302 study), ABX464 50mg once daily, right after the study visit.

A paper diary in which the patient should report the number of capsules taken and the intake time from baseline visit onwards, will be given to the patient at baseline.

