6.3. Study Discontinuation

All patients, regardless of the completion or premature discontinuation, should perform the End of Study Visit according to the study flow-chart.

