7.1. Definition of an AE

Any untoward medical occurrence in a patient or clinical investigation patient administered a pharmaceutical product and which does not necessarily have to have a causal relationship with this treatment.

An AE can therefore be any unfavorable and unintended sign (including an abnormal laboratory finding), symptom, or disease (new or exacerbated) temporally associated with the use of a medicinal product, whether or not considered related to the medicinal product.

Note: The official definition also extends to AEs occurring in the placebo arm. Because of regulatory requirements, events occurring during pre-and post-treatment periods will also be designated as AEs. Therefore, reporting of such events, AEs and SAEs, will commence when the patient is enrolled into the study (date of signature of the informed consent) up until 4 Weeks after the end of the treatment visits. The period after discontinuing study drug may be extended if there is a strong suspicion that the drug has not yet been eliminated.

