7.4. Time Period, and Frequency of Detecting AEs and SAEs

All AEs and SAEs occurring from the time a patient consents to participate in the study until 4 Weeks after he or she has completed or discontinued the investigational product must be recorded in the Patient's eCRF.

Moreover, any occurrence of pregnancy within 6 months post stopping dosing must be reported.

Importantly, SAEs will have to be reported, either by email or by Fax, to IntuVigilance Limited within 24 hours of awareness of an SAE.

IntuVigilance Limited

[name]

Hotline [contact]

Email Address: [contact]

[contact]

Legislative guidance requires the investigator to also ensure that any **related** SAEs are reported after the patient finished the study if the investigator becomes aware of them.

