11.6 SAFETY ANALYSES

11.6.1 Adverse Events

An overall summary table will be presented (any adverse event, any treatment emergent adverse event (TEAE), any serious adverse event (SAE), death, any grade 3 or higher adverse events from baseline to the end of Study) (*Table 14.3.1.1*). This analysis will be conducted on SAF population.

Primary safety endpoint, the rate of all treatment emergent adverse experiences, will be compared in subjects who received a given dose of ABX464 or placebo by likelihood ratio chi-square test on a 10% two-sided significance level (*14.3.1.2.1*).

Two periods will be defined for TEAE:

- Period I: any adverse event which occurs or worsens from first dosing to Day 84;
- Period II: any adverse event which occurs after Day 84.

Adverse events will be described by primary system organ class and preferred term according to the two periods. Numbers and percentage of patients, and number of occurrences of adverse event will be presented for:

- TEAE (Table 14.3.1.2.2 and Table Table 14.3.1.2.3);
- Serious TEAE (Table 14.3.1.3.1 and Table Table 14.3.1.3.2);
- TEAE leading to drug discontinuation (Table 14.3.1.4.1 and Table Table 14.3.1.4.2);
- TEAE of grade 3 or 4 (Table 14.3.1.5.1 and Table Table 14.3.1.5.2);

Further assessment of safety will be based on the frequency of adverse events (with and without regard to causality) graded according to the CTC-AE Classification and also, the review of individual values for clinical laboratory data, vital signs and ECG focusing on the detection of abnormal values and PCSAs [potentially clinically significant abnormalities (PCSAs) determined upon investigator considerations].

Adverse events will be tabulated (counts and percentages) by group. All adverse events will be listed, and the data will be tabulated by body system/organ class. Adverse event tabulations will include all treatment emergent adverse events, which will be further classified by severity, and relationship to treatment and dose level.

All adverse events (AE) will be classified using the version of the MedDRA coding dictionary specified in the DHM.

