Events will be classified as treatment-emergent if they started or increased in severity on or after the first date and time of medication dosing at Visit 1 and up to study closure or withdrawal date. If an event start date is partial, then the start day, month, year or stop date will be used to determine if the event is treatment-emergent. If the classification of the AE cannot be determined from the data available, then the event will be considered treatment-emergent.

Treatment-emergent adverse events (TEAEs) will be further classified as follows:

Severe TEAEs: Severity classified as 'severe' (Common Toxicity Criteria [CTC] grade 3 or 4) or missing.

Serious TEAEs: Serious classified as 'yes' or missing.

Drug-related TEAEs: Relationship to study drug classified as 'related' or missing.

Serious drug-related TEAEs: Both serious and drug-related, as specified above.

TEAEs leading to withdrawal from study: Action taken classified as 'discontinued'.

All AE summary tables will show the number (%) of patients having at least one event and the number of events in each treatment group and overall. Median duration of AEs (from baseline to occurrence) will be presented in the tables. Note: If a patient has multiple AEs with the same preferred term, these will be summarised once within the count for N (%) of patients, but each event will be counted within the number of reports n of each AE. Changes in severity of the same AE (if collected) will be counted only once within the number of reports n of each AE.

The following will be presented in listing format within the data summaries:

- Deaths (Table 14.3.2.1);

- Serious Adverse Events (*Table 14.3.2.2*);
- Adverse Events which Led to Withdrawal (*Table 14.3.2.3*).

All adverse events (including non-treatment-emergent events) recorded on the CRF will be listed within the data listings.

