14 LIST OF TABLES, FIGURES AND LISTINGS

14.1 LIST OF TABLES

Demographic Data

Table 14.1.1	Screening Failures	All Enrolled Patients
Table 14.1.2	Patient Disposition	All Randomised Patients
Table 14.1.3	Study Termination and Primary Reason for Withdrawal	All Randomised Patients
Table 14.1.4	Demographic and Baseline Characteristics	Full Analysis Set
Table 14.1.5.1	Medical History	Full Analysis Set
Table 14.1.5.2	Current Medical Conditions	Full Analysis Set

Efficacy Data

Table 14.2.1.1	Analysis of ACR20 Response Rate	Efficacy Set 1
Table 14.2.1.2	Analysis of ACR20 Response Rate	Efficacy Set 2
Table 14.2.1.3	Analysis of ACR20 Response Rate	PP Set
Table 14.2.2.1	Summary of Categorical ACR20 Response at Week 12	Efficacy Set 1
Table 14.2.2.2	Summary of Categorical ACR20 Response at Week 12	Efficacy Set 2
Table 14.2.3.1	Analysis of the individual components of the ACR20 response	Efficacy Set 1
Table 14.2.3.2	Analysis of the individual components of the ACR20 response	Efficacy Set 2
Table 14.2.4.1.1	Analysis of ESR	Efficacy Set 1
Table 14.2.4.1.2	Analysis of ESR	Efficacy Set 2
Table 14.2.4.2.1	Analysis of DAS28-CRP	Efficacy Set 1
Table 14.2.4.2.2	Analysis of DAS28-CRP	Efficacy Set 2
Table 14.2.4.3.1	Analysis of DAS28-ESR	Efficacy Set 1
Table 14.2.4.3.2	Analysis of DAS28-ESR	Efficacy Set 2
Table 14.2.4.4.1	Analysis of SDAI Score	Efficacy Set 1
Table 14.2.4.4.2	Analysis of SDAI Score	Efficacy Set 2
Table 14.2.4.5.1	Analysis of CDAI Score	Efficacy Set 1

Table 14.2.4.5.2	Analysis of CDAI Score	Efficacy Set 2
Table 14.2.4.6.1	Summary of FACIT-Fatigue Score	Efficacy Set 1
Table 14.2.4.6.2	Summary of FACIT-Fatigue Score	Efficacy Set 2
Table 14.2.5.1	Summary of Patients Different Responses and Remissions	Efficacy Set 1
Table 14.2.5.2	Summary of Patients Different Responses and Remissions	Efficacy Set 2

Safety Data

Table 14.3.1.1	Summary of Adverse Events	Safety Set
Table 14.3.1.2.1	Analysis of all Treatment-Emergent Adverse Events	Safety Set
Table 14.3.1.2.2	Treatment-Emergent Adverse Events, by SOC and PT: Period 1	Safety Set
Table 14.3.1.2.3	Treatment-Emergent Adverse Events, by SOC and PT: Period 2	Safety Set
Table 14.3.1.3.1	Serious Treatment-Emergent Adverse Events, by SOC and PT: Period 1	Safety Set
Table 14.3.1.3.2	Serious Treatment-Emergent Adverse Events, by SOC and PT: Period 2	Safety Set
Table 14.3.1.4.1	Treatment-Emergent Adverse Events Leading to Study Drug Discontinuation, by SOC and PT: Period 1	Safety Set

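### The primary TEAE test does not stop when open-label ABX464-302 treatment starts, so events on open-label ABX464 50 mg can be counted under placebo

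*SAP*

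**What the plan says.** - **TEAE window.** SAP 11.6.1 runs it from first dosing "on or after the first date and time of medication dosing at Visit 1 and up to study closure or withdrawal date". It names no limit at the last dose, at Day 84 or at the first ABX464-302 dose.
- **Events after Day 84.** The same section makes them a TEAE period: "Period II: any adverse event which occurs after Day 84". That period has no stated end and does not exclude 302 entrants. The two periods are applied to the tables by system organ class and preferred term.
- **Primary test.** In SAP 11.6.1, "the rate of all treatment emergent adverse experiences, will be compared in subjects who received a given dose of ABX464 or placebo". The method is a likelihood ratio chi-square at 10% two-sided. The SAP 14.1 title of Table 14.3.1.2.1 is "Analysis of all Treatment-Emergent Adverse Events". Its shell is any TEAE, yes or no, with no period in the title or footnote.
- **Open-label drug.** Protocol 5.6.1: "Patient enrolled in the ABX464-302 maintenance study will start the study medication on Day 84 (301 study)/D0 (302 study), ABX464 50mg once daily". The last double-blind dose is on Day 83.
- **Adverse event recording.** Protocol 7.4 requires that events "until 4 Weeks after he or she has completed or discontinued the investigational product must be recorded". Protocol 7.1 sets a similar limit, "up until 4 Weeks after the end of the treatment visits". Neither makes an exception for 302 entrants.

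**The concern.** Four weeks from Day 83 reaches Day 111, so the recording window overlaps 28 days of open-label dosing (Days 84 to 111) in patients who roll over. A placebo patient whose first TEAE comes on open-label ABX464 would become a placebo case in the primary safety test. Patients randomised to 100 mg who move to 50 mg would have their later events attributed to 100 mg.

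Safety is the primary endpoint. Counting ABX464 events under placebo raises the placebo rate and pulls the comparison towards no difference, which is the unsafe direction for such a test.

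**Working it through.** **Inputs from the SAP (3.5 and 11.6.1).** TEAE rates 10% and 50%, 20 patients per arm, likelihood ratio chi-square, 10% two-sided, stated power 89%.

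**Assumptions not in the documents.** The 10% and 50% are rates to Day 84 (SAP 3.5 gives no window). Risk is constant over time. Everyone completes 12 weeks. The same share r of each arm enters 302, with r from 50% to 90%. After Day 84, entrants carry the ABX464 risk (50 mg taken as equal to the original dose) and all others the placebo risk.

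**The plan's own figure.** Normal approximation with pooled variance under the null:
- standard error under the null: √(2×0.3×0.7/20) = 0.1449
- standard error under the alternative: √((0.09+0.25)/20) = 0.1304
- z = (0.40 − 1.645×0.1449)/0.1304 = 1.24, so power is 0.892

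The stated 89% reproduces. Full enumeration of the likelihood ratio test gives 0.912, which is the reference below.

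**28-day risk of a first TEAE.**
- On ABX464: 1 − 0.5^(1/3) = 20.6%
- On placebo or off drug: 1 − 0.9^(1/3) = 3.5%

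**If entrants' events are counted to Day 111.** The share of patients event-free at Day 84 who stay event-free is s = r×0.794 + (1−r)×0.965. The placebo rate is 1 − 0.9s, the active rate 1 − 0.5s and the difference 0.4s.

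| Case | s | Active | Placebo | Difference (points) | Chance of p<0.10 |
|---|---|---|---|---|---|
| To Day 84 only | – | 50.0% | 10.0% | 40.0 | 0.912 |
| To Day 111, no rollover | 0.965 | 51.7% | 13.1% | 38.6 | 0.880 |
| To Day 111, r = 0.5 | 0.880 | 56.0% | 20.8% | 35.2 | 0.777 |
| To Day 111, r = 0.9 | 0.811 | 59.5% | 27.0% | 32.4 | 0.680 |

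The second row shows that the longer window alone, with nobody on open-label drug, already costs 1.4 points. Relative to that row, open-label drug adds 7.7 to 13.9 points to the placebo rate, or 1.5 to 2.8 patients in 20.

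**Other settings.**
- Recording stopped at Day 105: 36.3 to 34.2 points, chance 0.814 to 0.741.
- Assumed rates of 40% v 20%: the difference falls from 20 to 17.7–17.0 points, and the chance from 0.429 to 0.336–0.308.

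**If entrants are cut at Day 84** and the rest are followed off drug for 28 days, s = r + (1−r)×0.965. At r = 0.5 the difference is 0.4×0.983 = 39.3 points. At r = 0.9 it is 0.4×0.997 = 39.9 points. With unequal entry it is 38.6 points (90% of active, 50% of placebo) or 40.6 points (50% and 90%).

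**The case against.** The strongest defence is that 302 entrants leave this study at Day 84. ABX464-302 is a separate study with its own consent (Protocol 3.1.1 and 6.1). Protocol 5.2.5 asks for the End of Study visit only from early discontinuers and patients not entering 302. Protocol 7.5 collects adverse events at study visits, and entrants then have none in this study after Day 84. The clock in Protocol 7.4 starts when the product is completed or discontinued, and entrants are described as carrying on treatment.

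This reading is possible and it stands as such. A reader might infer from the SAP wording that open-label events will certainly be counted under placebo. The documents do not support that, because nothing says these events enter the 301 data.

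Nor do they settle the opposite. Protocol 6.3 says "All patients, regardless of the completion or premature discontinuation, should perform the End of Study Visit according to the study flow-chart", the footnote to SAP Table 14.1.3 defines completion by the follow-up visit, and Protocol 7.4 ties recording to the product, not to a visit.

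Two further points limit the concern. A reader might attribute the whole loss to open-label drug, but the no-rollover row shows that part of it comes from the longer window. A reader might also infer that a safety signal would be hidden. However, Table 14.3.1.2.2 already gives an untested row for any TEAE by arm to Day 84, and the serious, discontinuation and grade 3–4 tables are split in the same way. That row is nearly clean: open-label dosing can start on Day 84, or on Day 82 if the Week 12 visit is early.

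**Conclusion.** The gap is real. The primary TEAE test has no end at the start of open-label treatment, and the recording rule read literally allows open-label ABX464 events to count under placebo, and 50 mg events under 100 mg. Whether this happens depends on a data-flow decision that neither document states.

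If those events are counted, the loss is about 5 to 8 points of a 40-point difference, and the chance of p<0.10 falls from 0.912 to between 0.777 and 0.680. If entrants are cut at Day 84, the effect is under 1 point with equal entry and at most 1.4 points with the unequal entry examined. All of these figures rest on the assumed rollover share, constant risk and planning rates read as rates to Day 84.

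The tests are descriptive and unadjusted by design, so what is affected is the reported estimate and p-value of the primary endpoint, not a formal decision. The change should be made, but the plan is not invalid without it.

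**What to change.** In SAP 11.6.1 and Protocol 8.4:
- Restrict Table 14.3.1.2.1 to events that start or worsen from the first dose to the Week 12 visit (Day 84 for patients who stop early) and before any ABX464-302 dose. Say so in a footnote.
- Report later events descriptively by original arm, separating off-drug follow-up from events on 302 drug.
- State which study owns adverse events after the first 302 dose.

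The cost is one cut-off rule and a footnote. The Week 12 visit date is already planned for Listing 16.4.2, and 302 entry status is needed only to split the later events. The small downside is that off-drug follow-up events leave the primary test, though they are still reported. Closing the window only at the first 302 dose would keep them and still remove the open-label events, but would leave patients observed for different lengths of time.

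SAP 10.1 needs no change: its statement that treatment group is as randomised already sits in the paragraph on listings.

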7.5. Recording AEs and SAEs

Severity of AEs will be assessed according to CTC-AE Classification Version 5.0.

Patients will be asked to report all AEs as part of the procedures performed at each study visit. The site personnel will document all AEs in the patient's medical record. All AEs subsequently must be recorded in the appropriate eCRF sections.

The following points must be recorded for each event:

- A description of the event in medical terms, not as reported by the patient;
- Date of onset (start date);
- Date of resolution (stop date);
- The time of onset with respect to administering the investigational product;
- The severity of the sign/symptom or clinically significant abnormal laboratory value according to CTC-AE Classification Version 5.0;
- The causal relationship between the investigational product and the occurrence of each AE. This will be assessed by each investigator using clinical judgment. Alternative causes, such as natural history of the underlying diseases, concomitant medications, other risk factors and the temporal relationship of the event to the investigational product will have to be considered. The causality of all AEs should be assessed by the investigator with the following question: Is there a reasonable possibility that the AE may have been caused by the investigational product? And answered "NO" (if not related) and "YES" (if related);
- Action taken regarding the investigational product:
 - No action;
 - Temporary discontinuation;
 - Permanent discontinuation;
 - Patient's outcome:
 - Recovered without sequelae / resolved without sequelae;
 - Recovered with sequelae / resolved with sequelae;
 - Recovering/Resolving;
 - On-going;
 - Fatal (for SAEs only).

If in any one patient, the same AE occurs on several occasions, the AE in question must be documented and assessed a new each time.

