5 DEFINITIONS AND DERIVED VARIABLES

5.1 DEFINITIONS

Study Drug: Study drug is taken to mean either ABX464 or placebo.

Baseline: Baseline is defined by patient and by variable as the last non-missing value before the first dose of study drug

Study Day: Study day is the number of days since start of treatment where the date of first dose is counted as Day 0.

Treatment Exposure: Treatment exposure is the number of days during the treatment period that the patient was exposed to the study treatment and is calculated as:

$$(\text{Date_of_last_dose}) - (\text{Date_of_first_dose}) + 1$$

Compliance: Compliance is the number of doses actually taken divided by the scheduled number of doses expressed as a percentage.

Non-compliance: Non-compliance is defined as taking less than 80% or more than 120% of study medication.

Protocol Deviation: a deviation related to study inclusion or exclusion criteria, conduct of the trial, patient management or patient assessment. This refers to any change, divergence, or departure from the study design or procedures defined in the protocol. Deviations recorded by the Project Manager or CRA, or detected by Data Management or by Statistical programming checks as described in Section 6.3 will be identified and discussed at the Data Review Meeting before database lock to agree which should be included in Listing I6.2.2.

Screening and enrollment: Screening is the process of active evaluation of potential participants for enrollment in a trial. After a patient is recruited, screening occurs during the enrollment period to see if they meet the inclusion and exclusion criteria. If they meet the criteria, the subject is eligible to enroll in the trial.

Baseline and Screening failure: A patient is considered to be a baseline failure if the patient signs the informed consent but withdraws before the screening visit. A patient who does not fulfil the randomization criteria will be considered as a screening failure.

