Table 14.2.5.1 Summary of Patients Achieving Different Responses and Remissions (Efficacy Set 1)

		ABX-464 100mg (N=xx)	ABX-464 50mg (N=xx)	Placebo (N=xx)
ARC20 Response				
Week 2	N	xx	xx	xx
	Rate	xx.x %	xx.x %	xx.x %
	Stratified 95% CI	xx.x % - xx.x %	xx.x % - xx.x %	xx.x % - xx.x %
Week 4	N	xx	xx	xx
	Rate	xx.x %	xx.x %	xx.x %
	Stratified 95% CI	xx.x % - xx.x %	xx.x % - xx.x %	xx.x % - xx.x %
Etc				
Etc				

Source: Listing 16.4.5.3
Path\Filename

Page x/y

Programmer's Note: List of variables consists of ACR20/50/70 response, Categorical DAS28-CRP response, LDA, DAS28-ESR remission, ACR/EULAR remission, SDAI remission, CDAI remission.

This layout also applies to:

Table 14.2.5.2 Summary of Patients Achieving Different Responses and Remissions (Efficacy Set 2)

ABX464-301

ddMMMyyyy

Table 14.3.1.1 Summary of Adverse Events (Safety Set)

	ABX-464 100mg (N=xx)		ABX-464 50mg (N=xx)		Placebo (N=xx)		Total (N=xx)	
	n	N (%)	n	N (%)	n	N (%)	n	N (%)
Any Adverse Event	xx	xx (xx.x%)	xx	xx (xx.x%)	xx	xx (xx.x%)	xx	xx (xx.x%)
Any Treatment-Emergent Adverse Event	xx	xx (xx.x%)	xx	xx (xx.x%)	xx	xx (xx.x%)	xx	xx (xx.x%)
Any Serious Adverse Event	xx	xx (xx.x%)	xx	xx (xx.x%)	xx	xx (xx.x%)	xx	xx (xx.x%)
Adverse Event leading to death	xx	xx (xx.x%)	xx	xx (xx.x%)	xx	xx (xx.x%)	xx	xx (xx.x%)
Any grade 3 or higher Adverse Event	xx	xx (xx.x%)	xx	xx (xx.x%)	xx	xx (xx.x%)	xx	xx (xx.x%)

The table presents number of events (n) and number and percentage of patients (N(%)).
The denominator for each percentage is the number of patients within the column.

Source: Listing 16.2.7
Path\Filename

Page x/y

ABX464-301

ddMMMyyyy

Table 14.3.1.2.1 Analysis of Treatment-Emergent Adverse Events (Safety Set)

		ABX-464 100mg (N=xx)	ABX-464 50mg (N=xx)	Placebo (N=xx)	p-value
Any Treatment-Emergent Adverse Event	N	xx	xx	xx	
	Yes	xx (xx.x%)	xx (xx.x%)	xx (xx.x%)	
	No	xx (xx.x%)	xx (xx.x%)	xx (xx.x%)	
Chi-squared test					x.xxxx

The denominator for each percentage is the number of patients within the column
TEAE rate between treatments is compared using likelihood ratio chi-square test at a two-sided 10% significance level.

Source: Listing 16.2.7
Path\Filename

Page x/y

ABX464-301

ddMMMyyyy

Table 14.3.1.2.2 Treatment-Emergent Adverse Events, by SOC and PT: Period 1 (Safety Set)

	ABX-464 100mg (N=xx)			ABX-464 100mg (N=xx)			Placebo (N=xx)			Total (N=xx)		
	n	N (%)	duration (days)	n	N (%)	duration (days)	n	N (%)	duration (days)	n	N (%)	duration (days)

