Any Treatment-Emergent Adverse Event	xx	xx (xx.x%)		xx	xx (xx.x%)		xx	xx (xx.x%)		xx	xx (xx.x%)	
SOC	xx	xx (xx.x%)	xx.xx	xx	xx (xx.x%)	xx.xx	xx	xx (xx.x%)	xx.xx	xx	xx (xx.x%)	xx.xx
PT	xx	xx (xx.x%)	xx.xx	xx	xx (xx.x%)	xx.xx	xx	xx (xx.x%)	xx.xx	xx	xx (xx.x%)	xx.xx
PT	xx	xx (xx.x%)	xx.xx	xx	xx (xx.x%)	xx.xx	xx	xx (xx.x%)	xx.xx	xx	xx (xx.x%)	xx.xx
SOC Etc	xx	xx (xx.x%)	xx.xx	xx	xx (xx.x%)	xx.xx	xx	xx (xx.x%)	xx.xx	xx	xx (xx.x%)	xx.xx
Etc												

The table presents number of events (n) and number and percentage of patients (N(%)).
The denominator for each percentage is the number of patients within the column.
Duration (days) represents median duration of AEs (from baseline to occurrence).

Source: Listing 16.2.7
Path\Filename

Page x/y

This layout also applies to:

Table 14.3.1.2.3 Treatment-Emergent Adverse Events, by SOC and PT: Period 2 (Safety Set)

Table 14.3.1.3.1 Serious Treatment-Emergent Adverse Events, by SOC and PT: Period 1 (Safety Set)

Table 14.3.1.3.2 Serious Treatment-Emergent Adverse Events, by SOC and PT: Period 2 (Safety Set)

Table 14.3.1.4.1 Treatment-Emergent Adverse Events Leading to Study Drug Discontinuation, by SOC and PT: Period 1 (Safety Set)

Table 14.3.1.4.2 Treatment-Emergent Adverse Events Leading to Study Drug Discontinuation, by SOC and PT: Period 2 (Safety Set)

Table 14.3.1.5.1 Treatment-Emergent Adverse Events of Grade 3 or 4 by SOC and PT: Period 1 (Safety Set)

Table 14.3.1.5.2 Treatment-Emergent Adverse Events of Grade 3 or 4 by SOC and PT: Period 2 (Safety Set)

ABX464-301

ddMMyyyy

Table 14.3.2.1 Listing of Deaths (Safety Set)

Treatment	Patient number	Date of death	Cause of death
xxxxxx	xxx-xxxx	ddMMyyyy	xxxxxxxxxxxxxxxxxxxx
xxxxxx	xxx-xxxx	ddMMyyyy	xxxxxxxxxxxxxxxxxxxx
Etc			

Path\filename

Page x/y

ABX464-301

ddMMMyyyy

Table 14.3.2.2 Listing of Serious Adverse Events

Treatment	Centre/ Patient number	Adverse Event PT SOC	Onset date	Resolution date / ongoing	Outcome	Relationship to study drug	Action taken with study drug	Other action taken
xxxxx	xxx-xxxx	xxxxxxxxxx xxxxxxxx xxxx	ddMMMyyyy	ddMMMyyyy / ongoing	Resolved/ Resolved without sequelae/ Etc	Yes/No	None/ Temporary discontinuation/ Etc	Concomitant medication (CM no.)/ Procedure (PR no.)
		xxxxxxxxxx xxxxxxxx xxxx	ddMMMyyyy	ddMMMyyyy / ongoing	Resolved/ Resolved without sequelae/ Etc	Yes/No	None/ Temporary discontinuation/ Etc	Concomitant medication (CM no.)/ Procedure (PR no.)
		Etc						
Etc								

Path\Filename

Page x/y

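### In eight TEAE tables the column headed duration is defined as baseline to occurrence, which is time to onset, so label and formula contradict each other

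*SAP*

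**What the plan says.** SAP section 11.6.1, in the paragraph on the layout of the AE summary tables, says: "Median duration of AEs (from baseline to occurrence) will be presented in the tables".

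SAP section 15 repeats this in the shell titled "Table 14.3.1.2.2 Treatment-Emergent Adverse Events, by SOC and PT: Period 1 (Safety Set". That shell has a column headed duration (days) for each treatment group and for the total. Its footnote reads: "Duration (days) represents median duration of AEs (from baseline to occurrence". The shell names Listing 16.2.7 as its source and says the layout also serves seven further tables, from "Table 14.3.1.2.3 Treatment-Emergent Adverse Events, by SOC and PT: Period 2 (Safety Set" to "Table 14.3.1.5.2 Treatment-Emergent Adverse Events of Grade 3 or 4 by SOC and PT: Period 2 (Safety Set".

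SAP section 5.1 fixes the day count: "Study day is the number of days since start of treatment where the date of first dose is counted as Day 0". SAP section 11.6.1 splits the tables by time. The first part is "Period I: any adverse event which occurs or worsens from first dosing to Day 84"; Period II takes events occurring after Day 84.

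Protocol section 7.5 requires an onset date for each event and also "Date of resolution (stop date". Listing 16.2.7 carries baseline date, onset date, and resolution date or ongoing status. The SAP defines no other statistic for AE duration or for time to onset.

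**The concern.** The length of an event runs from onset to resolution. The interval the SAP specifies runs from the start of treatment to onset, and the resolution date does not enter it. Heading and definition therefore describe two different quantities.

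The wording appears in both the methods text and the shell, so a programmer who follows the plan will produce onset day under a duration heading. SAP section 12 calls for independent programming of unique tables. Two programmers working from the same definition would agree with each other, so that check is unlikely to expose the mismatch.

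Safety is the primary objective of this trial, and these are its main descriptive tables of event type. A reader who takes the heading at face value would see brief events that begin late as prolonged, and long events that begin early as short.

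**Working it through.** The plan states no numerical result that depends on this definition, so there is no figure to reproduce. The check counts the tables affected, derives the range of values the definition allows, and compares the two statistics on assumed events.

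**Tables affected.** One shell plus seven tables that reuse it: 1 + 7 = 8.

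- All TEAEs: 14.3.1.2.2 and 14.3.1.2.3
- Serious TEAEs: 14.3.1.3.1 and 14.3.1.3.2
- TEAEs leading to drug discontinuation: 14.3.1.4.1 and 14.3.1.4.2
- Grade 3 or 4 TEAEs: 14.3.1.5.1 and 14.3.1.5.2

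Each pair is one Period 1 and one Period 2 table, so four of the eight are Period 2. Tables 14.3.1.1 and 14.3.1.2.1 have no such column.

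**Range of printed values.** Inputs: first dose is Day 0 (SAP 5.1), and the baseline visit is the first dosing day (Protocol 5.2.2). Hence

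printed value = onset date − baseline date = study day of onset.

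- An event that starts in Period 1 prints 0 to 84.
- An event in Period 2 starts after Day 84, so it prints 85 or more.

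**Longest Period 2 event observable in the window.** Inputs: the last dose for a patient who completes treatment is on Day 83 (Protocol 5.6.1); AEs are recorded until 4 weeks after treatment ends (Protocol 7.4); the end-of-study visit is Day 105 ± 2 (Protocol 5.2.5).

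- End of AE recording: 83 + 28 = Day 111.
- Latest end-of-study visit: 105 + 2 = Day 107.
- Event starting on Day 85 and followed to Day 111: 111 − 85 + 1 = 27 days.
- The same event followed to Day 107: 107 − 85 + 1 = 23 days.

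So the smallest value that can appear in a Period 2 table (85) exceeds the longest event length observable in that window (27). For an event starting on Day 85 really to last 85 days, it would have to be followed to Day 85 + 85 − 1 = 169, which is 169 − 111 = 58 days beyond the recording window.

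**Illustration with assumed events** (onset day, resolution day), with length taken as resolution − onset + 1:

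| Period | Assumed events | Median as the SAP defines it | Lengths | Median length |
|---|---|---|---|---|
| 1 | (3, 5), (40, 42), (70, 73) | 40 days | 3, 3, 4 | 3 days |
| 2 | (86, 88), (90, 91), (100, 103) | 90 days | 3, 2, 4 | 3 days |

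These events are invented to show the mechanism. They do not forecast the trial's data.

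**The case against.** The best answer is that this is a poor label and the statistic itself is sound. The definition is given twice in matching words, once in the text and once in the footnote. Listing 16.2.7, the stated source, has a baseline date column, which time to onset needs and event length does not. On that reading the authors meant time to onset and chose the wrong noun. This is plausible and the documents do not rule it out. A reader might infer that the formula is the error and that the SAP reports the wrong statistic; that goes further than the text allows. What stands on either reading is that heading and definition cannot both be right.

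The second answer is that little is lost. The footnote prints the definition under each table, so a careful reader can see what was calculated. Event lengths can be recovered from Listing 16.2.7, and for serious events from Table 14.3.2.2. Neither event length nor time to onset is listed as an endpoint. The Period 2 values would be too large to pass as lengths of events that began after Day 84. All of this stands, and it keeps the point minor. It does not help the Period 1 tables, where values of 0 to 84 look credible as durations.

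A reader might also infer that the protocol makes headaches lasting more than a week an event of special interest, so that this column bears directly on them. Protocol section 5.3.2 does not say that. It names headache episodes and skin lesions in general as events of interest. The one-week threshold, joined with failure of standard painkillers, only triggers a questionnaire, and that questionnaire asks separately how many days the headaches last.

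Finally, the column shows medians. An extreme case, such as a one-day event starting on Day 70 printing as 70, appears in that form only in a cell with a single event.

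**Conclusion.** The point holds as a contradiction between label and definition in SAP section 11.6.1 and in the shell used for eight tables. Followed literally, the plan would report onset day as AE duration in each group and in the total. In the four Period 2 tables every value would be at least 85 days, against a maximum of about 27 days observable within the window. That comparison assumes that baseline is the day of first dose, that the last dose is on Day 83, and that AE recording ends 4 weeks later. Protocol section 7.1 allows the period to be extended, but it would have to run to Day 169 before even the earliest Period 2 event could last as long as its printed value.

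Which quantity was intended cannot be settled from the documents. The effect is limited to one descriptive column. A reader might infer that the safety conclusions are at risk, but the TEAE counts and percentages, and the likelihood ratio chi-square comparison in Table 14.3.1.2.1, do not use it. This is a minor correction, worth making because it is cheap and because these tables serve the primary objective.

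**What to change.** Before database lock, state which statistic is meant and make the SAP text, column heading and footnote agree.

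- If event length is meant: compute resolution date minus onset date plus 1. Report the number of ongoing events beside the median, and state how they are handled. Leaving them out without comment would understate length.
- If time to onset is meant: rename the column and correct the wording in section 11.6.1 and in the footnote. The calculation stays as it is.
- If both are wanted: give each its own correctly named column.

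In every case, state whether the median is taken over events or over patients, and which date applies to an event that worsened after first dose. Give a rule for partial dates as well; section 11.6.1 covers these only for deciding whether an event is treatment-emergent.

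The cost is either a relabel or one derivation with its rules for ongoing events and partial dates. Onset and resolution dates are already collected, so no new data and no protocol amendment are needed. The small downside is that the ongoing-event and partial-date rules must be written and agreed before lock.
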